8.2. Statistical method

8.2.1. Modification of the clinical decision chest physiotherapy

Calculation of the net reclassification index (NRI) (29):

$$\text{NRI (\%)} = (P_{\text{upevents}} - P_{\text{downevents}}) - (P_{\text{upnonevents}} - P_{\text{downnonevents}})$$

With:

Events: the results of the lung and diaphragm US are compatible with the clinical diagnosis for a clinical hypothesis.

Non Events: the results of the lung and diaphragm US are not compatible with the clinical diagnosis for a clinical hypothesis.

P_{upevents}: number of «events» when the LUS results modified the chest physiotherapy treatment modalities divided by the total number of «events».

P_{downevents}: number of «events» when the LUS results didn't modify the chest physiotherapy treatment modalities divided by the total number of «events».

P_{upnonevents}: number of «non-events» when the LUS results modified the chest physiotherapy treatment modalities divided by the total number of «non-events».

P_{downnonevents}: number of «non-events» when the LUS results didn't modify the chest physiotherapy treatment modalities divided by the total number of «non-events».

The significance test used will be the correlated proportions test (use of the properties of multinomial distribution). This is an asymptotic test for the hypothesis $NRI=0$.

$$z = \frac{\widehat{NRI}}{\sqrt{\frac{\hat{p}_{up,events} + \hat{p}_{down,events}}{\# \text{ events}} + \frac{\hat{p}_{up,nonevents} + \hat{p}_{down,nonevents}}{\# \text{ nonevents}}}}$$

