As an alternative to the CT-scan, lung ultrasound (LUS) presents greater sensitivity and specificity than chest X-ray in the diagnosis of these same diseases. LUS can also be used to assess the diaphragm with greater accuracy and reproducibility than is the case using routine

measurement tools which often provide only global measures of respiratory dysfunction (Maximal Inspiratory Pressure (MIP). Whereas, LUS can also be used to identify diaphragm dysfunction (both bilateral and unilateral dysfunction) with excellent sensitivity and specificity compared with standard of transdiaphragmatic measurements of pressure(10).

Physiotherapists working in critical care may be developing the skills to undertake LUS to assess their patients (9, 10). Lung and diaphragm US assessments may allow them to determine the optimal indications for chest physiotherapy and thus avoid unnecessary or inappropriate treatments (9, 10). The information provided by LUS may modify the physiotherapist's therapeutic management. Given the relatively recent discussions on the use of lung and diaphragm US in chest physiotherapy (11,12), the usefulness of this tool for physiotherapy in critical care has never been evaluated. Xirouchaki et al. (13)assessed the impact of LUS on clinical decisions in critically-ill patients by intensivists and demonstrated that it significantly affected the medical diagnosis and modified the therapeutic management. Also a recent case report highlighted the impact of LUS on the clinical decision-making by physiotherapists in critical care (14). As far as we are aware, no study has prospectively and systematically evaluated the impact of the information provided by LUS on clinical-decision making by physiotherapists in the use of chest physiotherapy in patients hospitalized in an ICU.

2. Researchhypothesis

The lung and diaphragm ultrasound findings provided to the physiotherapist will modify his/her clinical decision-making in regards to chest physiotherapy treatment in the critical care patient.

3. Objectives

3.1.Principal objective

The principal objective of this study is to evaluate the impact of using the results of lung and diaphragm US on clinical decisions by physiotherapists regarding chest physiotherapy in patients hospitalized in an ICU.

3.2.Secondary objectives

The secondary objectives are to:

1. Determine whether LUS has an impact on clinical decisions in chest physiotherapy:

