 - When the findings from a chest CT-scan less than 12hours old are available;
 - For each clinical hypotheses;
 - For each level of certainty of clinical hypothesis;
 - For type of patients (reasons for admission the most represented);
 - For each research center.
2. Determine the level of agreement between the physiotherapist's diagnosis comparing the clinical vs LUS findings, overall, for the level of certainty of clinical diagnosis and for the population where a CT-scan is available;
3. Determine the frequency of changes in the chest physiotherapy following the assessment of the LUS results, overall and for each type of clinical hypothesis;
4. Determine the frequency of changes in the medical treatment (determined by intensivist) following the assessment of the LUS results performed by the physiotherapist, overall and for each type of clinical hypothesis.

4. Judgement criteria

4.1.Principal judgement criterion

Modification of the clinical decision: agreement (yes/no) between the lung and diaphragm US diagnosis and the clinical diagnosis and modification (yes/no) of the chest physiotherapy protocol, expressed using the Net Reclassification Index (NRI).

4.2.Secondary clinical decision-makingjudgementcriteria

1. Modification of the clinical decision:
 - When a chest CT-scan < 12h is available;
 - For each clinical hypotheses;
 - For the level of certainty of clinical hypotheses (Likert scale: strongly certain, certain, neither certain nor uncertain, uncertain, strongly uncertain);

- For type of patients (reasons for admission the most represented);
 - For each research center.
2. Proportion of agreement between clinical and LUS diagnosis:
- Overall;
 - For the level of certainty of clinical hypotheses (Likert scale: strongly certain, certain, neither certain nor uncertain, uncertain, strongly uncertain);
 - When chest CT-scan < 12h is available.
3. Proportion of cases when the chest physiotherapy protocol is modified following the results of the LUS:
- Overall;
 - For each type of clinical hypothesis;
 - When a chest CT-scan < 12h is available;
4. Modification of the clinical decision of intensivist:
- Overall;
 - For each type of clinical hypothesis;
 - When a chest CT-scan < 12h is available.

5. Inclusion/exclusion criteria:

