8.2.3. Agreement between clinical and LUS diagnosis

Calculation of Kappa index:

The clinical diagnosis and the lung ultrasound allow to diagnose the following events : (the retained airway secretions and bronchospasm diagnoses aren't included in the analysis as LUS doesn't allow their diagnosis (LUS may only be compatible with these hypotheses):

- T1: pneumonia/consolidation;
- T2: atelectasis (~~passive or active mechanism~~ obstructive);
- T3: pleural effusion;
- T4: pulmonary edema or global interstitial syndrome;
- T5: pneumothorax;
- T6: reduced aeration at the most dependent parts of the lungs;
- T7: diaphragm dysfunction (unilateral or bilateral);
- T8: examination is inconclusive.

Contingency table:

		Lung ultrasound								Total
		T1	T2	T3	T4	T5	T6	T7	T8	
Clinical diagnosis	T1									
	T2									
	T3									
	T4									
	T5									
	T6									
	T7									
	T8									
Total										

Proportion of observed agreement:

$$P_a = \frac{1}{n} \sum_{i=1}^p n_{ii}$$

Theoretical proportion of observed agreement:

$$P_e = \frac{1}{n^2} \sum_{i=1}^p n_{i.} \cdot n_{.i}$$

Kappa :

$$\kappa = \frac{P_a - P_e}{1 - P_e}$$

The Kappa index will be calculated for the global population, the population where the clinical diagnosis is « strongly certain/certain » and « strongly uncertain/uncertain » and the population with a CT-scan < 12h.

8.2.4. Proportion of cases when the chest physiotherapy protocol is modified following the results of the LUS:

Calculation of proportion: $P_{\text{upevents}} + P_{\text{upnonevents}}$ for all of the clinical hypothesis, for each clinical hypothesis and in the CT-scan <12h subpopulation.

With a confidence interval at $\alpha=0.05$.

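### The primary NRI does not measure how often ultrasound changes treatment, the 8.2.4 sum is not a proportion, and 8.2.5 plans no frequency for the intensivist

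*Combined protocol and SAP*

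**What the plan says.** The research hypothesis in section 2 is this: "The lung and diaphragm ultrasound findings provided to the physiotherapist will modify his/her clinical decision-making". The principal criterion in 4.1 has two parts, "agreement (yes/no) between the lung and diaphragm US diagnosis and the clinical diagnosis and modification (yes/no) of the chest physiotherapy protocol", and is expressed as a net reclassification index (NRI).

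Section 8.2.1 defines the two groups by compatibility of the scan: "Events: the results of the lung and diaphragm US are compatible with the clinical diagnosis for a clinical hypothesis"; non-events are the incompatible cases. Within each group, up is the share whose treatment was modified and down the share whose treatment was not. For events, down is "number of «events» when the LUS results didn't modify the chest physiotherapy treatment modalities divided by the total number of «events". The index is (up - down) in events minus (up - down) in non-events, with a z statistic: "This is an asymptotic test for the hypothesis $NRI=0". Section 8.2.2 repeats the index in every subgroup.

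Secondary criterion 3 in 4.2 is the "Proportion of cases when the chest physiotherapy protocol is modified following the results of the LUS". Its formula in 8.2.4 reads "Calculation of proportion: $P_{\text{upevents}} + P_{\text{upnonevents}}$ for all of the clinical hypothesis, for each clinical hypothesis", with a confidence interval at alpha 0.05.

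Secondary objective 4 is to "Determine the frequency of changes in the medical treatment (determined by intensivist) following the assessment of the LUS results". Section 8.2.5 gives only the index, with the groups redefined by the intensivist's diagnosis.

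Section 8.1 expects an NRI of 30%, asks for at least 50 events, and aims for 150 patients. There an event is a modified decision, whereas in 8.2.1 it is a compatible scan.

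**The concern.** If modified and not modified exhaust each group, the index can only compare modification rates between compatible and incompatible scans. It is zero when ultrasound changes treatment in 2% of both groups and zero when it changes treatment in 96% of both. A test of NRI = 0 then says nothing about the section 2 hypothesis. A null result could be read as ultrasound having no effect on decisions when it changed many of them, and a significant one could come from few changes.

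The fallback would be the secondary proportion, but 8.2.4 adds two fractions with different denominators. For the intensivist there is no fallback statistic at all.

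**Working it through.** **The plan's own figure.** Inputs from 8.1: NRI 30%, 50 events (modifications), N = 150. The only simple route from one to the other reads 30% as a modification rate, which 8.1 does not say. Then N = 50/0.30 = 166.7, so 167, not 150. In reverse, 150 x 0.30 = 45 modifications are expected, and the binomial chance of at least 50 is 21%. A total of 150 needs a rate of 50/150 = 1/3. The 150 is not reproduced.

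**The index.** Let p_e and p_ne be the modification rates in compatible and non-compatible cases, and n_e and n_ne the group sizes. From 8.2.1, down = 1 - up in each group, so

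NRI = (2p_e - 1) - (2p_ne - 1) = 2(p_e - p_ne).

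This needs no assumption. The overall modification rate is (n_e p_e + n_ne p_ne)/(n_e + n_ne), which the index does not determine.

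**Same rate, different index.** The documents give no group split; 100 compatible and 50 not is an assumption.

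| Modified, compatible (of 100) | Modified, not compatible (of 50) | Overall rate | Index | 8.2.4 sum |
|---|---|---|---|---|
| 10 | 35 | 45/150 = 30% | 2(0.10 - 0.70) = -120% | 80% |
| 30 | 15 | 30% | 2(0.30 - 0.30) = 0% | 60% |
| 35 | 10 | 30% | 2(0.35 - 0.20) = +30% | 55% |
| 40 | 5 | 30% | 2(0.40 - 0.10) = +60% | 50% |
| 30 | 40 | 70/150 = 46.7% | 2(0.30 - 0.80) = -100% | 110% |

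**Same index, different rate.** An index of +30% means p_e - p_ne = 0.15, with p_ne anywhere from 0 to 0.85. At 75/75 the overall rate runs from 0.5 x 0.15 = 7.5% to 0.5 x 1 + 0.5 x 0.85 = 92.5%, or about 11 to 139 of 150 patients. At 100/50 it runs from 10% to 95%.

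**The 8.2.4 sum.** Let w = n_e/(n_e + n_ne). The sum minus the true rate is (1 - w)p_e + w p_ne. With both groups non-empty this is positive whenever any treatment is modified. At 75/75 the sum is always double the true rate. Its range is 0 to 2, and above 1 no binomial interval exists.

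**Sign.** A positive index means more changes when the scan agrees with the clinician than when it disagrees. If discordant scans change treatment more often, it is negative. Annexe 2b lists some of the same options under different hypotheses, so a discordant scan need not change treatment. The documents do not settle the direction and do not explain the expected 30%.

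**The test (minor).** Since up + down = 1, the z denominator is always sqrt(1/n_e + 1/n_ne). At an index of 0.30, z = 0.30/sqrt(2/75) = 1.84 at 75/75, and 0.30/sqrt(1/100 + 1/50) = 1.73 at 100/50; both are below 1.96. Under equal rates p, the standard error should be 2 sqrt(p(1 - p)(1/n_e + 1/n_ne)), which matches only at p = 0.5. Exact two-sided size at 1.96, with the pooled two-proportion test in brackets:

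| Split | p = 0.3 | p = 0.4 | p = 0.5 |
|---|---|---|---|
| 75/75 | 2.6% (4.9%) | 3.7% (5.5%) | 4.1% (5.5%) |
| 100/50 | 3.7% (5.1%) | 5.2% (5.2%) | 5.65% (5.65%) |

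**The case against.** The best defence is 4.1 itself. It names agreement and modification together, and a contrast of modification by agreement uses exactly those two items. The contrast also ties change to the ultrasound result, whereas a raw before/after share counts every change whatever its cause. The frequency of physiotherapy changes is planned separately as a secondary outcome, its meaning is clear from the 8.2.4 heading, and all the counts will exist. For the intensivist, 8.2.5 defines both group rates, so the frequency could be derived.

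Much of this stands. The contrast is a legitimate quantity, and which measure is primary is the sponsor's choice. The attribution limit is real, and no information is lost. But 4.1 is headed as modification of the decision, and the contrast alone cannot speak to that or to section 2. The clear intent of 8.2.4 does not correct its formula: a result of 110% would be noticed, but 60% in place of 30% might not be. For objective 4, a figure that could be derived is not a planned output with an interval.

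The missing sign for the 30% shows an undefined expectation rather than an error. The 45, 21% and 167 figures hold only under the modification-rate reading. The pilot label does not excuse the formulas, since the modification rate is what this study should supply, and section 10 makes a later randomised trial depend on positive results.

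**Conclusion.** The concern holds, and the formulas are wrong as written. That the index equals 2(p_e - p_ne), and that the 8.2.4 sum is not a proportion, follow from the plan's definitions alone. Followed literally, the plan leaves the section 2 hypothesis untested by its primary test, reports too high a figure for objective 3 whenever both groups are non-empty and any treatment changes, and gives no overall figure for objective 4. The fault carries into every subgroup in 8.2.2.

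The numerical examples assume 150 patients, one record each, and the stated splits. Section 8.2.1 does not state the unit of analysis; section 6.5.1.5, which sets treatment for the primary hypothesis, supports one record per patient. The test-size point is minor and would not by itself require a change.

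**What to change.** 1. **8.2.4:** replace the sum by (modified among compatible + modified among non-compatible)/all analysed patients, one record per patient for the primary hypothesis, with a Wilson or exact 95% interval.
2. **4.1 and 8.2.1:** report this overall rate with the two group rates. Either make the overall rate primary, or keep both parts of 4.1 and co-report the rate with the contrast. State that a before/after share cannot attribute each change to the ultrasound, and tabulate beside it the reasons for change that 7.4.5 already records.
3. **If the contrast is kept:** define it as the rate in non-compatible cases minus the rate in compatible cases. Do not call it an NRI or read its test as a test of whether ultrasound modifies decisions. Use the pooled variance for the test and the unpooled variance for the interval. The pooled test holds its size better at lower rates, but it too can slightly exceed 5%.
4. **8.2.2 and 8.2.5:** apply the same measures, so that 8.2.5 yields the frequency in objective 4.
5. **8.1:** give *event* one meaning and restate N = 150 as precision: 45/150 has a Wilson 95% interval of 23.2% to 37.8%, and 50/150 one of 26.3% to 41.2%.
6. **Compatibility:** take it from the yes/no agreement in 4.1, or derive it by a written rule from the recorded primary hypothesis and ultrasound diagnosis.

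The cost is a documented amendment to the primary measure and the sample-size wording, plus a few lines of code on counts that 8.2.1 already requires. No extra patients or procedures are needed. If data are already collected, declare the change as post hoc and report the planned index alongside.

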6.5.1.4. Clinical hypotheses

Following the examination, he/she will put forward one or several hypotheses concerning the respiratory dysfunction (and not the medical diagnosis) and will either confirm or refute the indications for chest physiotherapy (*cf. annexe 2a*). If chest physiotherapy is indicated, the physiotherapist will specify the protocol to be used. The choice of the treatment modalities with regard to the type of respiratory dysfunction is detailed in annexe 2b.

According to the clinical examination, the clinical physiotherapist formulates one or more of the following clinical hypothesis (*cf annexe 2a*):

- Clinical examination is compatible with retained airway secretions;
- Clinical examination is compatible with bronchospasm;

- Clinical examination is compatible with pneumonia/consolidation;
- Clinical examination is compatible with atelectasis (~~passive or obstructive~~active mechanism);
-
- Clinical examination is compatible with pleural effusion;
- Clinical examination is compatible with pulmonary edema or global interstitial syndrome;
- Clinical examination is compatible with pneumothorax;
- Clinical examination is compatible with reduced aeration at the most dependent parts of the lungs;
- Clinical examination is compatible with unilateral diaphragm dysfunction (~~unilateral or bilateral~~);
- Clinical examination is compatible with bilateral diaphragm dysfunction;
- Clinical examination is inconclusive.

Among the formulated clinical hypotheses, the clinical physiotherapist will choose one primary clinical hypothesis (the choice is left to the discretion of the clinical physiotherapist, based on the probability and priority of the clinical hypothesis in terms of treatment).

A lung and diaphragm US will be done (see below) following the evaluation of the clinical physiotherapist with the physiotherapist who undertakes the US assessment blinded to the clinical assessment findings of the clinical physiotherapist. The clinical physiotherapist will then incorporate the results of the lung and diaphragm US and deem whether they are compatible with the clinical hypotheses put forward. He/she will then specify the chest physiotherapy protocol according to the results of the US-scan.

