6.5.1.5. Choice of chest physiotherapy treatment

The clinical physiotherapist will define the chest physiotherapy treatment modalities according to the formulated clinical hypothesis. The following treatments may be proposed :

- No chest physiotherapy treatment indicated;
- Refer to the intensivist;
- Non-invasive ventilation;
- CPAP (if non-ventilated patient) or PEEP modifications (if ventilated patient);
- Manual or ventilator hyperinflation;
- Mechanical in-exsufflator (Cough Assist ©);
- Rib cage compressions, manual assisted cough;
- Endo or naso-tracheal suctioning;
- Positioning;

- Semirecumbent position (head 45° from bed);
- Laterocubitus;
- Early mobilization:
 - Sitting on side of bed;
 - Standing;
 - Sitting on chair.

The choice of treatment according to the clinical hypothesis is defined in annexe 2b. The clinical physiotherapist will define the chest physiotherapy treatment modalities for the primary clinical hypothesis. The chest physiotherapy treatment modalities will be defined both before and again separately after the LUS and Diaphragm US examination.

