7.4.3. Initial clinical physiotherapist visit

The clinical physiotherapist undertakes the patient clinical examination, reviews the chest x-rays and additional tests as available. Moreover, he/she reviews the CT-scan if performed < 12h at the patient's admission including the radiology report. Following the clinical examination, the clinical physiotherapist formulates his/her clinical hypotheses. Among this formulated clinical hypotheses, the physiotherapist chooses a primary clinical hypotheses (the choice is left to the discretion of the clinical physiotherapist, based on the probability and priority of the clinical hypothesis in term of treatment). The primary clinical hypothesis and the secondary clinical hypotheses (if adapted) will be recorded in the case report form (CRF). According the primary clinical hypothesis, the clinical physiotherapist records his chest physiotherapy treatment modalities in the CRF.

The following data will be recorded:

- Medical management:
 - o Hypnotics ~~(and dose)~~;
 - o Opiates ~~(and dose)~~;
 - o Steroids ~~(and dose)~~;
 - o Anti-hypertensives ~~(and dose)~~;
 - o Antibiotics ~~(and dose)~~;
 - o Oxygen therapy (and flow);
 - o Mechanical ventilation, NIV (PEEP, IPAP, O₂ dose);
 - o Tracheotomy;
- Severity score: SAPSOFA
- Vital signs: RR, HR, BP SpO₂, FiO₂ (true or estimated), body temperature, RASS, Glasgow coma score;
- Clinical hypotheses of the clinical physiotherapist;
- Choice of chest physiotherapy protocol (before LUS).

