8.1. Calcul of number of subject

This is a pilot study and we don't have any information about the proportion of clinical decision modification in chest physiotherapy when the physiotherapist uses LUS information. The clinical experience of the investigators ([name] and [name]) allows to estimate an expected NRI of 30%. We want at least 50 events (clinical decision modification). So, we aim to include 150 patients in this study.

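### The variance in the primary NRI z-test is wrong under the plan's own definitions: its denominator does not depend on the modification rate

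*Combined protocol and SAP*

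**What the plan says.** Section 4.1 builds the principal criterion from two yes/no items: whether the ultrasound and clinical diagnoses agree, and whether the physiotherapy plan changes. Section 8.2.1 calls agreement an 'event' and disagreement a 'non-event'. In each group 'up' is the share whose treatment was modified and 'down' the share whose treatment was not. For non-events, 'down' is the "number of «non-events» when the LUS results didn't modify the chest physiotherapy treatment modalities divided by the total number of «non-events".

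The test is described in these words: "The significance test used will be the correlated proportions test (use of the properties of multinomial distribution"). The section adds: "This is an asymptotic test for the hypothesis" that NRI equals zero. The printed z divides the NRI by the square root of (p_up + p_down)/#events for events plus (p_up + p_down)/#nonevents for non-events. No alpha or sidedness is given for it.

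Section 8.1 sets the size of the study: "We want at least 50 events (clinical decision modification"), with an expected NRI of 30% and 150 patients. It also says that the investigators lack "any information about the proportion of clinical decision modification in chest physiotherapy".

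On the unit of analysis, section 6.5.1.4 says that "the clinical physiotherapist formulates one or more of the following clinical hypothesis". Section 6.5.1.5 then says: "The clinical physiotherapist will define the chest physiotherapy treatment modalities for the primary clinical hypothesis". Section 7.4.3 agrees: "According the primary clinical hypothesis, the clinical physiotherapist records his chest physiotherapy treatment modalities in the CRF".

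**The concern.** 'Modified' and 'not modified' exhaust each group, so p_up + p_down cannot be anything but 1. The quantity that should carry the sampling variability of the modification rates is then a constant. The omitted term, (p_up − p_down)², would be zero if the null hypothesis made 'up' and 'down' equally frequent within each group. Here NRI = 0 requires only that the modification rate be the same in events and non-events. It does not require that rate to be 50%.

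This is the only significance test stated for the principal criterion. If its variance is too large, a real association between agreement and modification can be missed, and tables carrying different amounts of evidence get the same p-value. Section 10 makes a later randomised trial depend on a positive result here.

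**Working it through.** **Inputs.** From the plan: the definitions and z in 8.2.1; N = 150, at least 50 modifications and an expected NRI of 30% in 8.1. Assumed, because the plan does not give them: two-sided 5% (critical value 1.95996), one independent row per patient, and the event shares and modification rates shown.

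**The plan's own figure.** 50/150 gives a modification rate of 1/3, used below as the implied rate. A rate of 0.30 would need 50/0.30 = 167 patients. That mismatch is a separate matter and does not affect this point. Note that 'events' means modifications in 8.1 but agreement in 8.2.1.

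**Algebra.** Let p_e and p_n be the modification rates in events and non-events, and n_e and n_n the group sizes.

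- NRI = (2p_e − 1) − (2p_n − 1) = 2(p_e − p_n).
- Printed denominator: sqrt(1/n_e + 1/n_n).
- Multinomial variance of p_up − p_down: [p_up + p_down − (p_up − p_down)²]/n = [1 − (2p − 1)²]/n = 4p(1 − p)/n.
- Omitted term (2p − 1)²: 0.11 at p = 1/3, 0.36 at 20%, 0.64 at 10%, 0 at 50%.
- Under a common rate p, true SE / printed SE = 2·sqrt[p(1 − p)], which is at most 1.

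At a 75/75 split the printed SE is sqrt(2/75) = 0.1633, its smallest value for 150 patients. Significance then needs |NRI| > 1.96 × 0.1633 = 0.320, so an observed NRI of exactly 30% cannot be significant at any split or modification rate. The pooled z at 75/75 and |NRI| = 0.30 is 0.15/sqrt[p(1 − p) × 2/75]: 2.30 at an overall rate of 20%, 2.00 at 30% and 1.95 at 1/3. The printed z is 1.84 in all three cases.

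**Size.** Asymptotic size is 2·{1 − Φ(1.96/sqrt[4p(1 − p)])}. Exact size comes from enumerating two binomials, averaged over a random split with event share 1/2.

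| Common rate | Asymptotic, printed z | Exact, printed z | Exact, pooled z |
|---|---|---|---|
| 10% | 0.0011 | 0.0012 | 0.0497 |
| 20% | 0.0143 | 0.0140 | 0.0505 |
| 1/3 | 0.0376 | 0.0372 | 0.0507 |
| 50% | 0.0500 | 0.0493 | 0.0505 |

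**Power**, by the same enumeration. All rows have |NRI| = 0.30 except the last, which has 0.60.

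| Event share | Rates (events / non-events) | Expected modifications | Printed z | Pooled z |
|---|---|---|---|---|
| 1/2 | 25.8% / 40.8% | 50 | 44.5% | 49.8% |
| 2/3 | 28.3% / 43.3% | 50 | 40.5% | 45.4% |
| 1/3 | 23.3% / 38.3% | 50 | 40.2% | 45.1% |
| 1/2 | 15% / 30% | 34 | 43.5% | 60.2% |
| 1/2 | 10% / 25% | 26 | 42.8% | 69.0% |
| 1/2 | 5% / 20% | 19 | 41.4% | 82.4% |
| 1/2 | 20% / 50% | 52.5 | 96.8% | 97.6% |

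**Three illustrative tables**, 70 events and 80 non-events, each with NRI = −0.30. The printed SE is sqrt(1/70 + 1/80) = 0.1637, so z = −1.833 and p = 0.067 every time.

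| Modified (events vs non-events) | Pooled z | Pooled p | Fisher p | Correct SE of NRI | 95% CI |
|---|---|---|---|---|---|
| 21 vs 36 | −1.888 | 0.059 | 0.066 | 0.156 | −0.61 to 0.01 |
| 14 vs 28 | −2.041 | 0.041 | 0.047 | 0.143 | −0.58 to −0.02 |
| 7 vs 20 | −2.386 | 0.017 | 0.020 | 0.120 | −0.54 to −0.06 |

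**If the unit is not the patient.** Suppose several hypotheses per patient were pooled and fell in the same group. The printed z becomes liberal once the design effect exceeds 1/[4p(1 − p)]: 1.13 at 1/3, 1.56 at 20%, 2.78 at 10%. An unclustered chi-square would be liberal at any design effect above 1.

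**The case against.** The case against concerns materiality, not the algebra.

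- At the implied rate of 1/3 (event share 1/2) the printed z behaves much like Fisher's exact test: size 3.7% against 4.0%, and power 44.5% against 45.6%. In the 21 vs 36 table, the one nearest the planned 50 modifications, no test reaches 5%.
- The large losses arise at rates the plan does not aim for. With 34 modifications expected, the chance of reaching 50 is about 0.2%, and it is smaller still in the other two scenarios.
- The study expects ultrasound to change decisions, and Annexe 2b ties treatment to the hypothesis. A wide gap between agreement and disagreement is therefore plausible, and there the error hardly matters.
- A conservative test does not create false positives, and this is a pilot study.
- The root cause is the definition of 'down'. If the NRI were redefined, the variance would have to be revisited anyway.

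Most of this stands as a limit on size. It does not make the formula right. Section 8.1 says the modification proportion is unknown, so lower rates cannot be excluded. The protection against false positives depends on one row per patient, which 6.5.1.5 and 7.4.3 support but 8.2.1 does not state. Fisher's test, unlike the printed z, does not drift towards zero size as modification becomes rarer: in the 7 vs 20 table it gives 0.020 against 0.067.

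**Conclusion.** The concern holds. Under the definitions in 8.2.1 the printed variance is correct only when both modification rates are 50%, and is otherwise too large. With one independent row per patient and a two-sided 5% level, the test is mildly conservative at the implied rate of 1/3, costing about 5 points of power at |NRI| = 0.30. It becomes severely conservative at about 20% and below or, by symmetry, 80% and above. If modification depends strongly on agreement, the effect is negligible. If several hypotheses per patient were pooled, the direction could reverse.

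Correcting the formula does not by itself make the study well powered: power is still about 45–50% at |NRI| = 0.30 and a rate of 1/3. Nor does it settle whether this NRI, which measures association between agreement and modification, captures the impact named in section 3.1. The point should be fixed, and it is not fatal.

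**What to change.** In section 8.2.1:

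1. State that the analysis has one row per patient, based on the primary hypothesis.
2. Replace the z formula with the pooled two-proportion (chi-square) test on the 2×2 table of agreement by modification, or Fisher's exact test if a group is small.
3. Report the NRI with SE = 2·sqrt[p_e(1 − p_e)/n_e + p_n(1 − p_n)/n_n] and a confidence interval.
4. State alpha and sidedness.
5. If several hypotheses per patient are to be analysed, use a variance clustered by patient.

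Sections 8.2.2 and 8.2.5 give no test; if those NRIs are tested, use the same method. The cost is one formula and a few sentences, with no new data and no extra patients.
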